The full analysis set of data will be derived from the set of all randomized participants in an intention-to-treat (ITT) analysis. All outliers that are within the realm of biological plausibility will be included in the analysis and only obvious data errors (e.g., resulting from technical issues) will be excluded. No statistical imputations will replace missing data for the outcome measures (*data as observed*), per contemporary guidelines [3]. However, the linear mixed effects model (see below for further details) is a principled approach to addressing missing outcome data. The model permits the inclusion of all participants in the analysis with a follow-up value (regardless of missing timepoints within a condition, or a missing alternative condition). Statistical analysis will be performed blinded to participant allocation.

OUTCOMES, STATISTICAL METHODS, AND COVARIATES

Primary endpoint: The preregistered primary outcome for this trial will be a comparison of blood glucose values assessed over 180 minutes following consumption of exogenous ketones or a placebo. Data will be analyzed according to the ITT principle via a linear mixed effects model with fixed effects for time after supplement ingestion (i.e., 30, 60, 90, 120, 150, 180 minutes), condition (i.e., ketone monoester vs placebo), period (depending on which condition was conducted first), and an interaction between time and condition and time and period as well as the baseline value (assessed at “time 0” immediately before consumption of the supplement) as a covariate. A random intercept for each participant (ID) and a random slope for time on the interaction of ID and period will be included. If a participant has a baseline value missing, we will impute this as the average (mean) baseline value observed across participants. Model assumptions of normality and linearity will be assessed visually by inspecting a Q-Q plot, and homoscedasticity will be assessed by plotting residuals vs fitted values. Models will be run using log-transformed outcome variables when departure from model assumptions is observed.

In addition to the primary analysis detailed above, we will explore the primary endpoint via the following confirmatory analyses:

1. Paired t-test on blood glucose incremental area under the curve (i.e., glucose above baseline fasting values across 180 minutes after ingestion of supplement or placebo)

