2. Paired t-test on peak blood glucose concentration (i.e., highest blood glucose value measured after ingestion of supplement or placebo)
3. Paired t-test on peak blood glucose concentration above baseline (i.e., highest blood glucose value above fasting baseline after ingestion of supplement or placebo)
4. Paired t-test on blood glucose total area under the curve (i.e., glucose above zero across 180 minutes after ingestion of supplement or placebo)

Secondary outcome measures:

Secondary outcomes will be analyzed similarly to the primary outcome using a linear mixed effects model. Secondary and exploratory blood marker outcomes that are below or above the detection limit, will be imputed as limit of detection (LOD) / $\sqrt{2}$ or $LOD * \sqrt{2}$, respectively [4]. Preregistered secondary outcomes include:

1. Metabolic outcomes (plasma insulin, plasma c-peptide, plasma free fatty acids, plasma β -OHB)
2. Markers of brain/cognitive function (intracranial blood flow measured by ultrasound, blood pressure measured manually, cognitive function using BrainBaseline on an iPad, brain-derived neurotrophic factor)
3. Markers of inflammation (plasma tumour necrosis factor alpha, plasma interleukin-1 β , plasma interleukin-6, total blood monocytes and monocyte subsets, monocyte histone acetylation)
4. Markers of appetite (self-reported hunger and fullness assessed via a 0 to 100 mm Visual Analog Scale, gastrointestinal symptoms assessed via a 0 to 100 mm Visual Analog Scale, total energy consumed in kilocalories during a buffet style meal at the end of testing)

Exploratory outcomes measures:

Exploratory outcomes will be analyzed similarly to the primary outcome using a linear mixed effects model.

Exploratory outcomes that were not preregistered include:

1. Metabolomics
2. Electrolyte status, lactate, pH etc.

REPORTING RESULTS

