We will summarize data (including participant baseline characteristics) as mean \pm standard deviation (SD) for continuous and N (%) for categorical data. A significant effect will be concluded at two-sided P -value of < 0.05 . We will report on the effect of condition and the interaction of the treatment effect over time. Effect estimates from the model alongside 95% confidence intervals around the mean differences in the outcome after accounting for the included covariates will be reported. Changes in outcome within condition (e.g., effect of ketone monoester on blood glucose at 180 minutes compared to baseline) will be reported via mean differences with SD outside the model, if applicable. Effect sizes (Hedges' g) will be stated.

PROGRAMMING PLAN

Statistical analysis will be performed after the last patient out, using R [5].

REFERENCES

1. Myette-Côté, É., et al., Prior ingestion of exogenous ketone monoester attenuates the glycaemic response to an oral glucose tolerance test in healthy young individuals. *The Journal of Physiology*, 2018. **596**(8): p. 1385-1395.
2. Francois, M.E., et al., Combined interval training and post-exercise nutrition in type 2 diabetes: a randomized control trial. *Frontiers in Physiology*, 2017. **8**: p. 528.
3. Chakraborty H. A mixed model approach for intent-to-treat analysis in longitudinal clinical trials with missing values [Internet]. 2009. Available at: <http://www.rti.org/publication/mixed-model->

approach-intent-treat-analysis-longitudinal-clinical-trials-missing-values

4. Canales R.A., et al. Methods for handling left-censored data in quantitative microbial risk assessment. *Appl Environ Microbiol* 2018. **84**(20): e01203-18.
5. Team RC. A Language and Environment for Statistical Computing. R Foundation for Statistical Computing 2020. Available at (accessed November 4, 2021): <https://www.r-project.org/>
- 6.

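### The primary model gives time-0 glucose one slope for all six samples; if that slope weakens over 180 minutes, the ketone-placebo intervals are wider than they need be, mainly for time-specific contrasts and the condition-by-time interaction

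*SAP*

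**What the plan says.** The SAP (Outcomes, Statistical Methods, and Covariates, Primary endpoint) specifies "fixed effects for time after supplement ingestion (i.e., 30, 60, 90, 120, 150, 180 minutes"), plus condition and period. The terms allowed to vary with time are then listed: "an interaction between time and condition and time and period as well as the baseline value". The time-0 value, taken at each visit, enters "immediately before consumption of the supplement) as a covariate", which reads most naturally as one slope common to all six post-dose samples. No baseline-by-time term appears in either document.

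The random part is: "A random intercept for each participant (ID) and a random slope for time on the interaction of ID and period will be included". The time slope is therefore independent between a participant's two visits. The text does not say whether each visit also has its own random intercept.

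Under Reporting Results the SAP states: "We will report on the effect of condition and the interaction of the treatment effect over time", with 95% confidence intervals. The protocol's Statistical Analyses section also plans ketone-placebo comparisons at each time point. The model is reused elsewhere: "Secondary outcomes will be analyzed similarly to the primary outcome using a linear mixed effects model", and likewise for exploratory outcomes.

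**The concern.** A time-0 value may predict the 30-minute sample better than the 180-minute sample, and people who start high may drift down more as the fast continues. If so, the slope on baseline falls with time.

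That drift follows the participant's baseline, and the two baselines are correlated (the plan assumes r = 0.7 between repeated measures). Most of the drift is therefore the same at both visits and cancels in the within-person contrast. The model has no fixed term for it. It can only be absorbed by the participant-by-period slope variance, which the model treats as independent between visits and so charges in full to the error of the ketone contrast.

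What is at stake is precision. A real change in the glucose effect over the three hours becomes harder to detect, and late contrasts look less certain than they are.

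**Working it through.** **Inputs from the documents.** Fasting glucose 8.6, SD 2.3 mmol/L; r = 0.7; 15% reduction; 20 participants, two visits, six post-dose times. These reproduce the planning effect: 0.15 × 8.6 = 1.29 mmol/L, and 1.29 / (2.3 × √(2 × 0.3)) = 0.724, against the stated 0.73. The documents give no figure for how the baseline slope behaves over time.

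**Assumed inputs.** Visit intercept SD 0.4, visit slope SD 0.3 per 180 min, residual SD 0.3 mmol/L. Baseline slope 0.95 at 30 min, falling linearly by 0 to 30% at 180 min. A 20% fall means that someone 2.3 mmol/L above average loses 0.20 × 0.95 × 2.3 = 0.44 mmol/L of that excess.

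**Step 1: closed form for the 180-minus-30 change.** With complete, balanced data the single baseline adjustment drops out of this contrast. Let Δ be the fall in the baseline slope and S the baseline SD.

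- Visit slope variance over 150 min: (0.3 × 150/180)² = 0.0625. Residual part: 2 × 0.3² = 0.18. Sum: 0.2425.
- Constant slope: SE = √(2/20 × 0.2425) = 0.156.
- SAP model with a falling slope: SE ≈ √(2/20 × (0.2425 + Δ²S²)).
- True spread: √(2/20 × (0.2425 + (1 − r)Δ²S²)), because only the part not shared by the two visits remains.

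At S = 2.3:

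| Fall | Δ | Δ²S² | SAP-model SE | Ratio to 0.156 | True spread |
|---|---|---|---|---|---|
| 10% | 0.095 | 0.048 | 0.170 | 1.09 | 0.160 |
| 20% | 0.190 | 0.191 | 0.208 | 1.34 | 0.173 |
| 30% | 0.285 | 0.430 | 0.259 | 1.67 | 0.193 |

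REML fits to 500 simulated trials gave model SEs of 0.170, 0.206 and 0.256, against 0.156 with the interaction added. The simulated spreads were 0.170, 0.187 and 0.209: somewhat above the formula, but below the model SE at 20% and 30%. Part of the extra width is thus real loss of precision, and part is an overstated SE.

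At S = 1.2, Δ²S² is 0.052 (20% fall) and 0.117 (30% fall), giving ratios of 1.10 and 1.22.

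**Step 2: all three reported quantities.** SE inflation without versus with the interaction, by REML simulation, with a random intercept and slope per visit. Ranges are over separate runs of 80 to 500 data sets.

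| Baseline SD | Fall | Average effect | 180-min contrast | 180-minus-30 change |
|---|---|---|---|---|
| either | 0% | 0% | 0% | 0% |
| 2.3 | 20% | about 5% | about 16% | about 34% |
| 2.3 | 30% | 11–20% | 33–41% | 64–68% |
| 1.2 | 20% | 1% | 5% | 10% |
| 1.2 | 30% | 3% | 10% | 22% |

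**Step 3: other variances.** With residual SD 0.4, visit slope SD 0.5 and no separate visit intercept, a fall from 0.95 to 0.75 widened the 180-minute interval by 15–19% and that for the change by 12–18%. A fall from 0.95 to 0.55 gave coverage of 98.6–99.8% for these two results. Absolute bias never exceeded 0.03 mmol/L.

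**Step 4: the other reading of the random part.** If each visit has a random slope but no random intercept, the ordering changes: under the Step 2 assumptions at SD 2.3, a 20% fall widens the average effect most, by about 24%. Under this reading, adding the interaction alone leaves the average-effect SE too small when visits differ in level (0.107 against a true spread of 0.131). The visit intercept is needed too.

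**The case against.** One common baseline slope is an ordinary ANCOVA form, and nothing else in the documents contradicts it. Participants are fasted and no meal or glucose load is described during the 180 minutes, so a stable slope for glucose is plausible. In that case the model loses nothing. This stands: the harm is conditional.

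The planning SD of 2.3 comes from another study. Here HbA1c is limited to 6.5–8.0% and insulin users are excluded, so the SD could be smaller. At 1.2 (an assumed value) the inflation is small. This stands too, and is why both SDs are shown.

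A reader might infer that the main ketone comparison is underpowered or biased. The figures do not support that. With a random intercept and slope per visit at SD 2.3, the simulated average-effect SE was at most 0.171 (30% fall), so the planned effect is 1.29 / 0.171 = 7.5 SEs from zero. The estimates were essentially unbiased. The documents also set no target for a change in effect over time, so there is no planned power for the interaction to fall short of.

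A reader might also expect the problem to be worse for insulin, C-peptide, fatty acids or appetite. Neither document gives anything on which to judge that.

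The supporting paired t-tests on total and incremental AUC use within-person differences, so the shared trend largely cancels in them. They protect the overall effect, but not the time-specific contrasts or the interaction.

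**Conclusion.** The point holds as a conditional loss of precision that can be removed at almost no cost. The omission and the mechanism are clear from the model text. The size depends on three things that the documents do not settle: how far the baseline slope falls, this trial's baseline SD, and the visit-to-visit variances. Across the 20–30% falls examined under the Step 2 assumptions, widening of the 180-minus-30 change runs from about 10% to 68%. The average effect is little affected with an intercept and slope per visit, and most affected under a slope-only reading.

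The omitted term makes the analysis conservative; it does not create false positives. The understated SE noted for the slope-only reading is a separate matter, arising from a missing visit intercept. The change is worth making for the time-specific and interaction results, and does not call the primary conclusion into question.

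**What to change.** In the primary model, add a baseline-by-time interaction, with time as the six categorical sampling times and baseline centred at its mean. State that each participant-by-period has a random intercept as well as a random time slope. Report the average condition effect, the time-specific contrasts and the condition-by-time interaction at mean baseline. Apply the same terms to outcomes with repeated post-dose values that are analysed similarly.

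The cost is a sentence in the SAP and five extra fixed-effect parameters against up to 20 × 2 × 6 = 240 glucose values. There is no measurable loss of precision if the slope is constant, and no new data are needed. The SAP says that the trial was completed in November 2021. If the data are already unblinded, keep the specified model as primary and report this one as a labelled sensitivity analysis.

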A randomized placebo-controlled, cross-over pilot study in which 20 adults with type 2 diabetes will participate in two experimental trials. All participants will provide written informed consent during an initial familiarization visit.

Following screening, eligible participants (N=20) will participate in two experimental trials of β -OHB supplementation versus placebo with order of treatment balanced, separated by ~7 days. Pre-menopausal women will be tested in the follicular phase (days 3-9) to minimize any potential changes in insulin sensitivity across the menstrual cycle [8]. Participants will be asked to refrain from structured exercise and alcohol, and limit physical activity to their activities of daily living on the day before each trial. A standardized diet with ~50% energy from carbohydrate, ~30% fat, ~20% protein (energy based on Harris-Benedict equation with an activity factor of 1.4) will be oriented on the day before each trial. Participants will then fast overnight (8-10h) and refrain from taking any medications 24 hours before the morning of the trial. Upon arrival, an indwelling intravenous catheter will be inserted and a baseline fasting blood sample will be obtained. The oral β -OHB supplement or placebo will be consumed in liquid form (~20-25 mL). Both drinks are masked with a proprietary calorie-free strawberry flavour developed by H.V.M.N®, USA, which results in the same taste profile for each. The β -OHB supplement will provide 0.3 g/kg β -OHB in the form of the ketone monoester (*R*)-3-hydroxybutyl (*R*)-3-hydroxybutyrate (Δ G®, TDeltaS, Oxford, UK). We used this dose in our supporting pilot study and published work shows it can consistently raise blood β -OHB levels to ~2-3 mmol/L within 15-30 minute[9] [2] [10]. Post consumption of the β -OHB or placebo blood samples will be obtained at 30, 60, 90, 120, 150 and 180 minutes.

The primary outcomes will be total plasma glucose as represented by the 3-hour area under the curve. Secondary outcomes include plasma insulin and C-peptide levels, plasma free fatty acids (FFA), inflammatory cytokines, cerebral blood flow (CBF), cognitive function, BDNF, signalling molecules, self reported hunger and fullness by a Visual Analog Scale (VAS) and GI symptom questionnaire scores – all measured across 180 minutes post-supplementation.

Metabolite and hormone analyses

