The effect of acute exogenous oral ketone supplementation on blood glucose levels in type 2 diabetes

NCT 04194450

Version 7 – April 2, 2022 [H19-02947]

STATISTICAL ANALYSIS PLAN (SAP)

Exogenous Ketones in Type 2 Diabetes

Trial Registration: NCT04194450

Version 1: November 8, 2021 with dated adjustments up to April 2, 2022.

BACKGROUND AND AIM:

From December 2019 to November 2021, we completed the randomized crossover placebo-controlled study titled “Exogenous Ketones in Type 2 Diabetes”. The aim of the trial was to determine whether acutely ingesting exogenous ketones, in the form of a ketone monoester drink (0.3 g/kg (R)-3-hydroxybutyl (R)-3-hydroxybutyrate, Δ G®, TDeltaS, Oxford, UK, provided by HVMN), can lower blood glucose in individuals with type 2 diabetes (T2D). The trial also aimed to examine the impact of exogenous ketones on brain/cognitive function, measures of inflammation, and appetite. The primary outcome was plasma glucose concentration after consumption of exogenous ketones compared to ingestion of placebo assessed over 180 minutes following supplement consumption. It was hypothesized that consumption of exogenous ketones would lower blood glucose compared to the placebo.

SAMPLE SIZE CONSIDERATIONS

At the time of study design, there were no known studies evaluating the effect of acute supplementation with exogenous ketones in individuals with T2D. Therefore, we estimated sample size based on our pilot study in healthy volunteers, in which we saw a \sim 15% reduction in glucose area under the curve after ketone supplementation compared to placebo [1]. Using means and standard deviations for fasting glucose (8.6 ± 2.3 mM) from our previously published study in people with T2D ($N = 51$) [2], a 15% reduction in blood glucose corresponds to an effect size of $d = 0.73$. Assuming 80% power with an alpha level of 0.05 and a moderate correlation between repeated measures of $r = 0.7$, a total sample size of $N = 14$ is needed to detect differences between ketone and placebo conditions (calculated using G*Power v3.1). To preserve power

and account for any dropouts or missing blood samples, we aimed to recruit 20 participants, aiming for equal males and females.

ANALYSIS SET AND STUDY POPULATION

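### The SAP labels four paired t-tests on glucose confirmatory alongside the primary mixed model, under one P<0.05 rule, and does not say which test decides; one of the four is the protocol's own primary outcome

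*SAP*

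**What the plan says.** **Primary analysis.** SAP, Primary endpoint: "Data will be analyzed according to the ITT principle via a linear mixed effects model". The model has condition, time and period, the time-by-condition and time-by-period interactions, and the baseline value as covariate.

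**Further glucose tests.** The same section continues: "we will explore the primary endpoint via the following confirmatory analyses". Paired t-tests follow on (1) incremental AUC, (2) peak, (3) peak above baseline and (4) total AUC over 180 minutes. The SAP has separate headings for secondary and exploratory outcomes, but these tests stand under the primary endpoint.

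**Decision rule.** SAP, Reporting results: "A significant effect will be concluded at two-sided" P<0.05, not limited to any one analysis. From the model, "We will report on the effect of condition and the interaction of the treatment effect over time".

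**Protocol.** Experimental design: "The primary outcomes will be total plasma glucose as represented by the 3-hour area under the curve". The protocol's outcomes section instead describes the primary as glucose concentrations over the three hours. Neither place mentions incremental AUC, peak or peak above baseline.

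**Dates.** SAP title block: "Version 1: November 8, 2021 with dated adjustments up to April 2, 2022". SAP, Background and aim: "From December 2019 to November 2021, we completed the randomized crossover placebo-controlled study".

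**The concern.** One sentence uses two labels that conflict: an analysis that explores an endpoint does not confirm it. Here the label has consequences, because the only decision rule applies equally to the model and to each t-test. Nothing says what may be concluded if the model is not significant and a t-test is.

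Peak, peak above baseline and incremental AUC are different quantities from the model's adjusted glucose values, so they are not simply re-analyses of the primary. Total AUC raises a further difficulty. Someone reading the protocol could present a significant AUC test as the primary result even if the SAP's model had failed. Without a stated hierarchy, the report could lead with whichever result is favourable, and a reader could not tell which test the trial had staked its claim on.

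**Working it through.** **1. The plan's own figure.** The documents state no familywise error rate. Their one alpha-based figure is N = 14: "Assuming 80% power with an alpha level of 0.05", d = 0.73, r = 0.7.
- 0.15 × 8.6 / 2.3 = 0.561; divided by √(2 × (1 − 0.7)) = 0.775, this gives 0.724, close to the stated 0.73.
- An exact paired t-test with 0.73 gives N = 14 one-sided (power 0.826) and N = 17 two-sided (power at 14 is 0.714). With 20 participants the two-sided power is about 87%.

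So 14 reproduces exactly only for a one-sided test, which is a separate matter. What counts here is that the calculation budgets 0.05 for a single comparison.

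**2. Upper reference.** Five independent tests at 0.05: 1 − 0.95^5 = 22.6%. This is too high, because all five tests use the same blood samples and are correlated.

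**3. Null simulation of the crossover.** There were 72 settings with 20,000 trials each and no ketone effect.
- From the documents: glucose 8.6 (SD 2.3), r = 0.7, samples at 0 and at 30 to 180 minutes, n = 14 or 20.
- Assumed, because the documents do not give them: visit-level SD 0.5-1.26 mmol/L (the upper end is 2.3 × √(1 − 0.7) = 1.26), slope SD 0.3-1.0, residual SD 0.3-0.6, serial correlation 0-0.5, flat or falling mean, incremental AUC net or positive part only.
- Primary test: approximated by the paired contrast of mean post-drink glucose, adjusted for baseline and period. It is not a full fit of the mixed model.
- The four t-tests were run as the SAP describes them.

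| Which two-sided P<0.05 counts as a finding | Chance under no effect |
|---|---|
| Model's condition effect only | about 5% |
| Model or total AUC | 7.7-10.0% |
| Model or the three measures not in the protocol | 10.4-14.3% |
| Any of the four t-tests | 10.8-14.2% |
| Any of the five | 11.6-15.7% |
| Any of the five, or condition-by-time | 15.1-20.0% |
| A t-test significant, model not | 7.0-11.3% |
| Any of the five at 0.01 each (Bonferroni) | 2.5-3.6% |

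**4. Direction.** The hypothesis is that ketones lower glucose. Half of the any-of-five range is 5.8-7.9%. Counting only false lowering results directly, in four settings, gave 6.9-7.8%, against about 2.5% for the model's condition effect. The absolute risk is about half the two-sided figure; the relative inflation is much the same.

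**5. Inside the model.** The SAP reports both a condition effect and a condition-by-time interaction. With a simplified linear interaction test, the chance that at least one of the two is falsely significant is 8-10%. Resting the claim on the model therefore restores 5% only if one effect within it is named.

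**The case against.** The strongest reply is that the SAP does name one primary analysis and introduces the t-tests as additional to it. Its condition test has a 5% error rate, and correlated AUC and peak summaries are ordinary sensitivity analyses in a self-described pilot study. This largely stands. No sentence says that a t-test can override the model; the inflation arises only if one is allowed to carry the claim. But the confirmatory label and the general rule leave that open, and the SAP could have closed it in one sentence.

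A second reply is that the size cannot be derived from the documents. That stands too: it is a range under stated assumptions.

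Three stronger readings are tempting and are not supported.
- *The trial's error rate is 13% rather than 5%.* A reader might infer this, but it ignores the named primary and depends on assumed variances.
- *All four tests are late additions.* Total AUC is the primary outcome in the protocol's Experimental design section; only the other three are absent from the protocol.
- *The tests were chosen after seeing data, since the SAP is first dated in the month of completion.* The documents do not show whether the t-tests were in version 1 or came later, nor when the last visit took place. The SAP states that analysis is blinded to allocation and runs after the last patient out, and the protocol has plasma frozen for batch glucose assay. Blinding may be imperfect, because β-OHB is itself an outcome and is expected to reach about 2-3 mmol/L after the ketone drink. That is a reason to ask when condition was known, not evidence of selection.

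**Conclusion.** The concern holds as a defect of labelling and hierarchy. The SAP calls four further tests confirmatory, applies one significance rule to all, and does not say which test settles the glucose question, while the protocol's AUC primary appears as the fourth of them.

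If any of the five may support the claim, the two-sided error is about 12-16%, or about 7-8% against 2.5% for false lowering results; it is higher if the interaction also counts. These figures rest on assumed within-visit variances and on an approximation to the mixed model. If the model's condition effect alone decides, the rate is about 5% and the problem disappears. The change is worth making because it is cheap and removes the choice of which result to lead with.

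**What to change.** 1. **Reconcile the primary first.** State whether the decisive glucose test is the SAP's model or the AUC in the protocol's Experimental design section, and name a single test. One option is the model's condition effect averaged over 30 to 180 minutes, with a sentence on how total AUC relates to it. If the model is chosen, say that the condition-by-time test does not by itself establish the effect. Until this is settled, total AUC should not be barred from supporting the claim.
2. **Relabel.** In SAP, Primary endpoint, replace confirmatory analyses with supportive analyses, and add: *The incremental AUC and peak analyses, and whichever of the mixed model and total AUC is not the decisive test, are reported as estimates with 95% confidence intervals. They cannot establish a glucose effect if the decisive test is not significant.*
3. **Minor addition.** In the SAP title block, list each adjustment between 8 November 2021 and 2 April 2022 with its date, and say whether condition codes were known at the time.

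The cost is SAP wording plus the decision in step 1. No data or analyses are lost. The downside is a less favourable label for the supportive tests.

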Experimental Trial A (duration 210 minutes)

Females will complete experimental trials in the follicular phase. Participants will report to the laboratory after an overnight fast (8-10 hours). Adherence to the 24 hour diet will be confirmed upon arrival in the laboratory, as well as information about physical activity and sleep. An indwelling intravenous catheter will be inserted into the antecubital vein for repeated blood sampling by a trained phlebotomist ([name] and [name]). Blood (5 ml) will be drawn into EDTA tubes for measurement of plasma samples before being frozen in a -80 degree Celsius research refrigerator. There will be 7 intravenous blood draws in total for a total of ~35 ml of blood collected in each trial. The first collection will occur prior (0) to consumption of ketone or placebo drink. Another 6 blood draws will occur at 30 minute intervals (30, 60, 90, 120, 150, 180) after ingestion of the ketone or placebo drink. Thirty minutes after ingestion, participants will be instructed to complete the gastrointestinal distress questionnaire. Brain blood flow and blood pressure will be measured non-invasively and a cognitive test battery will be performed in separate intervals throughout the study. During the visit participants will answer a brief questionnaire regarding satiety and hunger. Subjects will be reminded to not perform exercise or to consume alcohol or medications 24 hours prior to the next visit.

Protocol timeline

Visit 2: Experimental Trial B

Subjects will return fasted to the laboratory at least 2 days after the first visit. Adherence to the 24 hour diet will be confirmed upon arrival in the laboratory. Participants will be instructed to identify any deviations in diet before beginning the second trial. Protocol for the second visit will be the same as visit 1, although participants will receive the remaining condition (ketone supplementation or placebo).

Statistical Analyses

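### Confirmatory analysis 1 does not say how glucose area below baseline counts; read literally, it can drop more than half of the planned lowering

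*SAP*

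**What the plan says.** The SAP (Outcomes, Statistical Methods, and Covariates) makes a mixed model of post-dose glucose the primary analysis. Its fixed effects include "an interaction between time and condition and time and period as well as the baseline value" as a covariate. It then adds four paired t-tests, introduced with "we will explore the primary endpoint via the following confirmatory analyses".

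- Item 1: "Paired t-test on blood glucose incremental area under the curve (i.e., glucose above baseline fasting values across 180 minutes" after the drink.
- Item 2: peak glucose.
- Item 3: peak above baseline, explained as "highest blood glucose value above fasting baseline after ingestion of supplement or placebo".
- Item 4: total AUC, explained as "glucose above zero across 180 minutes after ingestion of supplement or placebo".

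Neither document says whether area below baseline in item 1 is subtracted, ignored or set to zero, or whether a negative value in item 3 stays negative.

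Three design features bear on this. From the Protocol, Experimental Trial A: "Participants will report to the laboratory after an overnight fast (8-10 hours". From the Protocol, Experimental design: the supplement or "placebo will be consumed in liquid form (~20-25 mL", and participants "refrain from taking any medications 24 hours before the morning of the trial". The only meal mentioned is a buffet once testing is over (SAP, Secondary outcome measures).

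**The concern.** The hypothesis is that the supplement lowers glucose relative to placebo. In a fasted participant with no glucose load, that lowering goes below the participant's own baseline unless placebo glucose rises. An incremental AUC that counts only area above baseline discards that part.

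Two analysts following the SAP could therefore compute different quantities from the same seven samples. Under the literal reading, item 1 could show a much smaller difference than the primary model because of its definition and not because of the drink. The SAP also promises effect sizes (Hedges' g), so a shrunken estimate matters even where the test still rejects.

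**Working it through.** **Inputs.** From the Protocol (Sample Size) and SAP (Sample Size Considerations): fasting glucose 8.6, SD 2.3 mmol/L; 15% reduction; r = 0.7; 20 participants. From the Protocol (Experimental design): samples at 0 and every 30 minutes to 180. Not in the documents, so assumed and varied: the placebo course, the shape of the effect, and the variances of the 3-hour change.

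**1. The plan's own effect.** 0.15 × 8.6 = 1.29 mmol/L. 1.29 / 2.3 = 0.561, and 0.561 / √(2 × (1 − 0.7)) = 0.724, close to the stated d = 0.73. Over the sampling window, 1.29 × 180 = 232.2 mmol/L·min. Half of that is 116.1, or a mean of 0.645 mmol/L.

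**2. A bound that does not depend on curve shape.** Let P and K be the areas above baseline on placebo and ketone. Item 1, read literally, compares P − K. Since K cannot be negative, P − K is at most P. So if the placebo area above baseline averages less than 0.645 mmol/L, under half of the planned lowering is captured. While the ketone curve stays at or below baseline, K = 0 and the result is P alone, whatever the size of the effect.

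**3. Steady placebo rise of R by 180 minutes, constant lowering of 1.29, no noise.** P = 90R. K = 0 if R ≤ 1.29, otherwise K = 90(R − 1.29)²/R.

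| R (mmol/L) | P | K | P − K | Share of 232.2 |
|---|---|---|---|---|
| 0 or below | 0 | 0 | 0 | 0% |
| 0.5 | 45.0 | 0 | 45.0 | 19% |
| 1.0 | 90.0 | 0 | 90.0 | 39% |
| 1.29 | 116.1 | 0 | 116.1 | 50% |
| 1.5 | 135.0 | 2.6 | 132.4 | 57% |
| 2.0 | 180.0 | 22.7 | 157.3 | 68% |

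**4. Other shapes.** If placebo rises at once and stays up by R, P = 180R and the share is R/1.29 up to R = 1.29, so half is reached at 0.645. Allowing for slower onset and other effect shapes, half is reached at about 0.65–0.8. If the lowering wanes to zero with the same 3-hour average, a steady rise of 1.5 still captures only 42%.

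**5. With noise (simulation, all variances assumed).** Two sets were used. The narrower has drift SD 0.3–0.5 and residual SD 0.1–0.3. The wider goes up to participant SD 1, visit SD 1 and residual SD 0.5.

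- Flat placebo: 6–14% captured in the narrower set and up to about 33% across the wider settings. As a mean difference this is 0.06 × 1.29 = 0.08 to 0.33 × 1.29 = 0.43 mmol/L, instead of 1.29.
- Placebo falling by 1.0: 0–3% (narrower), 2–14% (wider).
- Steady rise of 1.29: 49–51% (wider).
- Halving the true effect, with placebo drift from −1.0 to +0.5, lowers item 1 by about 0–15% (narrower) or 24–33% (wider). Net area would drop by 50%.
- Power of item 1 with N = 20, full effect and flat placebo: roughly 81–100%. With placebo falling by 1.0: 4–67% in the narrower set.
- With no effect, item 1 rejects in 1–6% of simulated trials.

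**6. The signed alternative.** Net incremental AUC = total AUC − 180 × baseline. It captures the whole 232.2 for any placebo course.

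**The case against.** Items 1, 3 and 4 are worded alike. Glucose cannot be below zero, so in item 4 the word above can only name a reference line. Read the same way, item 1 is already net area and nothing is lost. This is a fair reading. It stands as a possibility, but the SAP does not state it.

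A reader might infer that any placebo rise of less than 1.3 mmol/L costs over half of the effect. The documents do not support that. The figure needs a steady rise and a lowering that persists; an early rise of 1.0 that stays up already captures more than half. Because medications are withheld, a placebo rise of some size cannot be ruled out.

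A reader might also infer that the trial's main result is at risk. It is not. The primary model is baseline-adjusted, item 4 counts all lowering, and the SAP (Reporting Results) provides for signed changes from baseline within each condition, so a fall below baseline should be visible. Positive-only area is a different summary, not a bias in the primary comparison.

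Finally, stating either convention would remove the ambiguity. That is correct. The reason to prefer net area is that it keeps the whole of the effect the trial was planned around.

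**Conclusion.** The point holds as a minor one. Item 1 lacks a rule for area below baseline. Under its literal reading, it captures under half of the planned 1.29 mmol/L lowering whenever placebo area above baseline averages less than about 0.65 mmol/L over the 3 hours. That covers flat placebo, falling placebo, and a steady rise of less than about 1.3 by 180 minutes.

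The bound follows from the plan's own 8.6 and 15%. The noisy shares (roughly 6–33% with flat placebo), the effect-halving figures and the power figures all rest on an assumed placebo course, curve shapes and variances. With a larger placebo rise the problem shrinks; under the reference-line reading it disappears. The harm is confined to a supportive analysis. The primary mixed model, total AUC and Type I error are unaffected.

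**What to change.** Define item 1 as net (signed) incremental AUC over 0–180 minutes, with area below baseline counted as negative (total AUC minus 180 × baseline). State that item 3 is a signed difference and is not set to zero when the peak lies below baseline. Leave items 2 and 4 and the primary model as they are.

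The cost is two wording changes and a recalculation from the same seven samples. The SAP says the trial was completed by November 2021, so the change should be dated. If the data are already unblinded, report the net version beside the above-baseline version and label it as added.

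There are two drawbacks: results become slightly less comparable with studies that report positive-only incremental AUC, and net area partly repeats the primary model's average condition effect.
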